3.1 Overview

This is a multicenter, participants-blinded, parallel-group, randomized controlled study conducted in China.

The participants will be recruited in 5 clinical sites, which are Guang'anmen Hospital, China Academy of Chinese Medical Sciences; Shaanxi Provincial Hospital of Traditional Chinese Medicine; Guangdong Provincial Hospital of Traditional Chinese Medicine; The First Hospital of Hunan University of Chinese Medicine; The Third Affiliated People's Hospital of Fujian University of Traditional Chinese Medicine. The study design and organization will be responsible by Guang'anmen Hospital, China Academy of Chinese Medical Sciences. A data coordination center will be established at Linkermed Pharm Technology Co., Ltd (Beijing, China) to monitor data management.

3.2 Eligibility criteria

3.2.1 Inclusion Criteria

- (1) Meet the requirements for a clinical diagnosis of DLSS combined with an MRI- or CT-based radiological diagnosis of central sagittal diameter stenosis of the lumbar spinal canal;
- (2) Have neurogenic intermittent claudication characterized by progressive pain of the buttocks and/or legs when standing or walking or with extension of the back, which are relieved upon sitting, lying down, or bending forward [20]; they always walk in flexion or hunchback posture;
- (3) Have pain of an intensity ≥ 4 in the buttocks and/or legs when walking, standing, or extending the back, as measured using the Numerical Rating Scale (NRS);
- (4) Have pain in the buttock and/or leg that is more severe than their pain in the lower back;
- (5) Have a Roland-Morris Disability Questionnaire (RMDQ) score of at least 7;
- (6) MRI (mainly) or CT scan showed the anterior posterior diameter of the canal was ≤ 12 mm;
- (7) Are aged 50-80 years;
- (8) Have provided signed consent and exhibit willingness to participate in the trial.

3.2.2 Exclusion Criteria

- (1) Congenital stenosis of the vertebral canal, indications of surgery for DLSS (e.g., segmental muscular atrophy, bowel and bladder disturbances), spinal instability requiring surgery, lumbar tuberculosis, lumbar metastatic carcinoma, vascular claudication, or vertebral body/vertebral stenosis segment compression fracture;
- (2) Severe vascular, pulmonary, or coronary artery disease with limited lower extremities motility;
- (3) Clinical comorbidities that could interfere with the collection of data related to pain and walking function such as fibromyalgia, chronic widespread pain, amputation, stroke, Parkinson's disease, spinal cord injury, and dementia;
- (4) Cognitive impairment, such that they are unable to understand the content of the assessment scales or provide accurate data;
- (5) A history of lumbar surgery;
- (6) Plans to become pregnant within 12 months or are already pregnant;
- (7) Received acupuncture treatments for DLSS within the previous 30days;
- (8) Neurogenic intermittent claudication mainly manifesting as numbness, weakness, or paresthesia of the lower extremities instead of pain.

4. Schedule of Evaluation

	Study Period								
	Enrollment/Allocation week		Post-allocation week						
			Treatment week			Follow-up			
Timepoints	Week -1		Week 0		1	2	3	4	5
Enrollment									
Eligibility screen	x								
Informed consent	x								
MRI/CT	x								
Demographics	x								
Expectancy of acupuncture	x								
Allocation		x							
Interventions									
Acupuncture			x	x	x	x	x	x	
Sham acupuncture			x	x	x	x	x	x	
Assessments									
RMDQ	x						x	x	x
NRS	x						x	x	x
SSSQ	x						x	x	x
HADS	x						x	x	x
Blinding assessment			x	x	x	x	x	x	x
Safety assessment			x	x	x	x	x	x	x

Table 1. Enrolment, Intervention and Evaluation Schedules

Abbreviations: MRI magnetic resonance imaging, CT computed tomography, RMDQ Roland-Morris Disability Questionnaire, NRS Numerical Rating Scale, SSSQ Swiss Spinal Stenosis Questionnaire, HADS Hospital Anxiety and Depression Scale

5. Efficacy and Safety outcomes

5.1 Efficacy outcomes

5.1.1 Primary Outcome

The primary outcome will be the change in the modified RMDQ score from baseline to week 6.

The RMDQ is a reliable pain-specific functional status questionnaire that is easy and simple for participants to complete [23]. The RMDQ includes 24 questions with a score range of 0–24. Notably, in this study, we will modify the response to “caused by low back or leg pain” for each question, which will be more suitable for participants who have sciatica [24, 25]. Disability is measured in terms of walking, standing, bending, working, sleeping, and activities of daily living. Higher scores indicate more severe symptoms, and a change in the score by 2.5 points is the minimal clinically important difference (MCID) for RMDQ scores [23]. A reduction of at least 30% and 50% reduction were additionally interpreted as minimal and substantial clinically meaningful improvement respectively [26, 27], which were adopted as secondary outcomes.

5.1.2 Secondary Outcomes

Secondary outcomes will include the following:

- (1) Changes in the RMDQ score from baseline to weeks 18 and 30;
- (2) The proportion of participants having at least 30% and 50% reductions in the RMDQ score from baseline to weeks 6, 18, and 30;
- (3) Changes in the average pain scores for the buttocks and/or legs when walking, standing, or extending the back as measured by the NRS in the previous 1 week from baseline to weeks 6, 18, and 30.

The NRS is a concise scale for assessing pain that is completed by the participants themselves. NRS scores range from 0 to 10 with 11 grades, and higher scores indicate greater pain [28, 29]. Two scales including one for measuring buttock and/or leg pain and another for measuring low back pain will be used (participants should answer with the average score for the previous 1 week). The degree of pain in the bilateral legs may be different, and data collection will be based on the degree of pain in the leg with more severe pain;

(4) The proportion of participants having at least 30% and 50% reductions from baseline in the average pain scores for the buttocks and/or legs when walking, standing, or extending the back, as measured by the NRS for the previous 1 week at weeks 6, 18, and 30;

(5) Changes in the average pain score for the lower back when walking, standing, or extending the back, as measured by the NRS for the previous 1 week from baseline to weeks 6, 18, and 30;

(6) Changes in the mean scores of the SSSQ for symptom severity and physical function from baseline to weeks 6, 18, and 30 and scores on the SSSQ satisfaction subscale at weeks 6, 18, and 30.

The SSSQ is a short outcome measure for symptoms and functions [30]. The SSSQ consists of 18 questions and three domains including symptom severity, physical function, and satisfaction with the degree of treatment. The scores for all three domains are calculated by taking the total score for the domain and dividing it by the number of answered questions, and if more than two items are missing, the scale scores for that domain are considered missing.

Six questions in the symptom severity domain assess pain of the back, buttocks, legs, or feet

as well as pain frequency, numbness, and weakness with scores ranging from 1 to 5, while one question assesses balance with possible scores of 1, 3, and 5. Higher scores indicate worse symptoms. The physical function domain assesses walking distance and ability to walk for pleasure, shopping, and getting around the house or apartment and from the bathroom to the bedroom. This domain has five questions with scores ranging from 1 to 4, and higher scores indicate less satisfaction. The satisfaction domain has four categories (very satisfied, somewhat satisfied, somewhat dissatisfied, and very dissatisfied) with a score range of 1–4 [31, 32].

(7) The proportion of participants who are somewhat satisfied and very satisfied based on the satisfaction domain of the SSSQ at weeks 6, 18, and 30;

According to satisfaction domain of the SSSQ, patients scoring 1.5-2.5 points are regarded as somewhat satisfied with the therapy, and those scoring 1.5 points or lower are regarded as very satisfied with the therapy [33].

(8) Changes in the HADS score from baseline to weeks 6, 18, and 30.

The HADS is validated and standardized for measuring the state of anxiety and depression [34, 35]. The HADS has two subscales with 14 items (7 items each), and a total score range of 0–21 with a range of 0–3 for each item. A score of ≥ 8 indicates the presence of anxiety and/or depression.

(9) Expectancy of acupuncture

Expectancy of acupuncture will be recorded at baseline. Participants will be required to answer two questions: “In general, do you believe acupuncture is effective for treating the illness?” and “Do you think acupuncture will help to improve your symptoms of DLSS?”

(10) Blinding assessment

Patients will be asked to answer the following questions after treatment (sessions 17 or 18) within 5 min: “Do you think you have received traditional acupuncture over the past 6 weeks?” The patients can answer “yes” or “no.”

(11) Safety assessment

Adverse events (AEs) related to acupuncture include severe pain, needle breakage, fainting, local hematoma, localized infection, and post-acupuncture discomfort with symptoms such as nausea, vomiting, palpitation, dizziness, headache, anorexia, and insomnia during the treatment period. AEs irrelevant to the treatment will also be recorded in detail throughout the trial.

5.2 Safety outcomes

According to their potential association with the treatment, AEs will be categorized as treatment-related or non-treatment-related within 24 hours after their occurrence. Treatment-related adverse events include pain, haematoma, localized infection, broken needle, fainting, nausea, headache, dizziness, insomnia, vomiting, or palpitations during or after treatment.

Serious AEs will be defined as events requiring hospitalization, causing disability or impaired ability to work, threatening life or resulting in death.

All the AEs and serious AEs, whether related to acupuncture or not, will be reported and documented.

6. Statistical Considerations

6.1 Study Hypothesis

The null hypothesis is that the change from baseline in the modified RMDQ score at week 6 would be the same for acupuncture and SA, and the alternative hypothesis was that the change would differ.

6.2 Statistical Analysis Set

The efficacy analyses will be done on the intention-to-treat (ITT) population, which will include all participants who will be randomized according to randomized treatment assignment. The safety analysis will be done on the safety population, which will include the ITT participants who received any treatment.

6.3 Statistical Analyses

6.3.1 The general principle

Summary Statistics

Summary tables (descriptive statistics and/or frequency tables) will be provided for all variables at different endpoints. For continuous variables, means and standard deviations will be presented, unless the variable has a skewed distribution, in which case medians, 25th and 75th percentiles will be presented. For categorical variables, the number and percentage of participants within each category will be presented. For each variable (continuous or categorical), the number of missing values will be reported.

Statistical Comparisons Between Groups

Continuous variables will be compared using a two-sample t-test or Wilcoxon rank-sum test if data show serious deviations from a normal distribution. Categorical data or ordinal data will be compared using a Chi-square test, Fisher's exact test or Wilcoxon rank-sum test, as appropriate.

For the analyses of the primary and secondary outcomes, estimated treatment differences and associated 95% two-sided confidence intervals will be presented.

Multicenter study

The study will be conducted by multiple investigators in 5 centers. The randomization sequence will be generated in varying blocking sizes and stratified by center. To estimate the overall variability of the center effects, we will perform a sensitivity analysis for the primary outcome.

Multiple Comparisons

For the analyses of the secondary and safety outcomes, no adjustment for multiple comparisons will be made.

Analysis Software

For all statistical analyses, SAS 9.4 software will be used. All hypothesis testing will be carried out at the 5% (2-sided) significance level.

6.3.2 Demographics and Baseline Characteristics

All data recorded at baseline will be summarized by group. Comparisons between groups will be performed using the methodology described in section 6.3.1. Summaries will be presented for the ITT set in both groups.

6.3.3 Analysis for Primary Outcome

The primary analysis will be conducted a mixed effects model for repeated measures (MMRM). In this model, the observed change from baseline score at each scheduled post-baseline visit will be the dependent variable. The model will include the baseline RMDQ score as a fixed effect, with categorical factors for treatment group (acupuncture and SA), visit and treatment \times visit interactions. The interactions will remain in the model regardless of significance. Treatment group comparisons at each visit will be estimated by differences between least squares (LS) means from the treatment \times visit interaction, with accompanying *P*-values and 95% CIs. An unstructured covariance pattern will be used to estimate the variance–covariance of the within-subject repeated measures. Parameters will be estimated using maximum likelihood with the Newton-Raphson algorithm and using the Kenward–Roger method for calculating the denominator degrees of freedom.

Sensitivity Analyses for the Primary Outcome

Multiple imputation will be used to impute missing values under the missing-at random assumption (MAR). Specifically, 100 imputed data sets will be generated using the fully conditional specification method or regression method with the number of iterations set to 10 for the following variables: group, baseline value and dependent variable. After multiple imputation, each of the hundred multiple imputation datasets will be analyzed using the MMRM model. The overall estimates will be calculated using Rubin's rules. The multiple imputation procedure (PROC MI) in SAS, version 9.4 will be used and *P*-value <0.05 will be considered statistically significant. To address potential center differences, we will incorporate site as either a fixed or random effect in the MMRM model.

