3.4 Study Time Frame

The duration of the study for each participant will be 31 weeks: 1 week before randomization as eligibility screening and baseline assessment, 6 weeks of treatment period, and 24 weeks of follow up period after the cessation of treatment (Figure 1. Study Design).

[figure not shown]

Figure 1. Study Design

There will be four timepoints of assessment:

Timepoint 1 will be scheduled during weeks -1 as eligibility screening and baseline assessment;

Timepoint 2 will be scheduled at week 6 at the end of treatment period;

Timepoints 3 and 4 will be scheduled at weeks 18 and 30, respectively, during 24-week follow-up period.

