6.1 Randomization

Patients who provide informed consent and are eligible will be randomly assigned at a ratio of 1:1 to either the acupuncture group or the SA group using a central randomization system. The randomization scheme will be generated by Linkerm Pharm Technology Co., Ltd (Beijing, China) using statistical analysis software SAS 9.4 with “proc plan” program. The randomization sequence will be generated in varying block sizes and stratified by center. A comprehensive document describing the randomization scheme will be sealed in opaque envelopes by the staff who produce it and kept by another staff who takes no part in the clinical trial. The randomization scheme will not be checked by anyone except the senior system administrator. In each clinical center, a research assistant who takes no part in the treatment and outcome assessment will log in the web-based central randomization system to assess the random number and group allocation. All randomization will be masked until all data analyses have been conducted.

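### Randomisation is stratified by centre, but the primary MMRM omits centre and is fitted by maximum likelihood: no bias and a small effect on the standard error, cheaply put right

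*Combined protocol and SAP*

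**What the plan says.** Protocol 6.1 states: "The randomization sequence will be generated in varying block sizes and stratified by center". SAP 6.3.1 repeats this ("The randomization sequence will be generated in varying blocking sizes and stratified by center") and adds: "To estimate the overall variability of the center effects, we will perform a sensitivity analysis for the primary outcome". There are five centres.

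SAP 6.3.3 defines the primary analysis as a mixed model for repeated measures (MMRM) in which "the observed change from baseline score at each scheduled post-baseline visit will be the dependent variable". Its terms are given as: "The model will include the baseline RMDQ score as a fixed effect, with categorical factors for treatment group (acupuncture and SA), visit and treatment" by visit. Centre is not among them. The covariance is unstructured. On fitting, the SAP says: "Parameters will be estimated using maximum likelihood with the Newton-Raphson algorithm", with Kenward-Roger denominator degrees of freedom.

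Centre returns only under the sensitivity analyses: "To address potential center differences, we will incorporate site as either a fixed or random effect in the MMRM model". Which of the two is not settled. SAP 6.3.4 carries the primary approach over to the other continuous outcomes.

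**The concern.** Two details of the specification pull the SE of the week-6 treatment difference in opposite directions.

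- **Centre.** Blocking within centre keeps the arms nearly balanced in each centre, so differences between centres largely drop out of the treatment contrast. A model without centre still counts those differences as residual variation, so its SE is larger than the true sampling SE.
- **ML.** ML divides by the number of patients without allowing for the mean parameters estimated, so its SE is too small. Kenward-Roger was developed for REML and does not repair this.

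The net direction depends on how much centres differ, which the plan does not state. At stake is whether the primary test runs at its nominal 5% level and whether the confidence interval is as narrow as the design allows. The sensitivity model with site does not change the primary test.

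**Working it through.** **Inputs.** Protocol 11.1: 98 per arm, difference 2.5, SD 5.5, two-sided 5%, power at least 80%, 20% dropout. SAP 6.3.1: five centres. Assumed, because the documents give no figures: centre ICC of 0 to 0.10 for the week-6 change after baseline adjustment; blocks of 4 or 6; centres of about equal size.

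**1. The plan's own figure.** Normal approximation: 2 × (1.960 + 0.842)² × (5.5/2.5)² = 76 per arm. The exact t calculation gives 77, and 77/0.8 = 96.25, so 97 per arm or 194 in total, against the stated 196. With 98 × 0.8 = 78.4 completers per arm, power is 80.7%. The sample size is sound.

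**2. Effect of ML.** The week-6 mean has 3 parameters (intercept, treatment, baseline). With 156 completers, ML SE / REML SE = √(153/156) = 0.990, about 1% too small. A small run of the three-visit MMRM with unstructured covariance gave 0.991, and the Kenward-Roger adjustment did not remove it.

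**3. Effect of omitting centre.** With many centres and perfect balance the SE would be inflated by 1/√(1 − ICC): 1.0%, 2.6% and 5.4% at ICC 0.02, 0.05 and 0.10. With five centres the pooled residual holds only about 4/5 of the between-centre variance, so the factor is √(1 + 0.8 × ICC/(1 − ICC)): 0.8%, 2.1% and 4.3%. Dropout disturbs the within-centre balance and reduces it further. Simulation of the week-6 contrast with 20% random dropout gave 0.6%, 1.7% and 3.4%.

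**4. Where the two cancel.** Setting (1 + 0.8 × ICC/(1 − ICC)) × (1 − 3/n) = 1 gives an ICC of 0.024 for n = 156 and 0.019 for n = 196. In simulation the crossing was near 0.018 without dropout and near 0.03 with 20% dropout. I would not state it more closely than 0.01-0.04.

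**5. Net result.** Week-6 simulation, 20,000 trials per setting, 196 randomised, 20% dropout, total SD 5.5:

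| ICC | Model SE / true SE, planned | Power, planned | Power, centre + REML |
|---|---|---|---|
| 0 | 0.991 | 80.9% | 80.3% |
| 0.02 | 0.997 | 81.3% | 81.0% |
| 0.05 | 1.008 | 81.8% | 82.3% |
| 0.10 | 1.025 | 82.5% | 84.4% |

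The mean error of the treatment estimate was at most 0.005 points in every setting. Across this simulation and a separate three-visit one, planned type I error lay between about 4.2% (ICC 0.10) and 5.2% (ICC 0). With centre and REML the SE ratio was 1.00 and type I error 4.8-5.1% in the week-6 simulation. Unequal centres (80/40/30/26/20) gave the same picture.

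**6. Changing only one of the two.** Fixed centre adds 4 parameters. Kept under ML, the ratio is √(149/156) = 0.977, so the SE is about 2-3% too small, and simulated type I error is about 5.3-5.8%. That is slightly worse than the current plan.

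**7. Centre × visit.** The model also covers the later visits: "Timepoints 3 and 4 will be scheduled at weeks 18 and 30, respectively, during 24-week follow-up period". A single centre effect removes all week-6 centre variation only if centre effects are constant over visits. In the three-visit simulation (156 complete cases, within-subject correlation 0.6 assumed), the 95% half-widths were:

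| ICC | Planned | Centre main effect, REML: centre effects constant / correlated 0.5 / independent over visits | Centre and centre × visit, REML |
|---|---|---|---|
| 0.05 | 1.72 | 1.70 / 1.71 / 1.72 | 1.70 |
| 0.10 | 1.71 | 1.65 / 1.68 / 1.70 | 1.65 |

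**The case against.** The best defence is that the plan does not ignore centre, because a site-adjusted sensitivity analysis is specified, and that what remains is largely preference. There is no bias, planned type I error is never far from 5%, and at an ICC of zero the proposed model has slightly less power than the planned one. With no ICC in the documents, even the direction of the net effect is unknown. All of that stands, and it is why this is a minor point. It does not remove the case for changing a line of text: the planned test sits at its nominal level only near one unknown ICC, while the adjusted test does so throughout.

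Three stronger readings are tempting and should not be drawn.

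- A reader might infer that ignoring the stratification factor invalidates or biases the primary comparison. It does neither. Above the crossing point the planned test is mildly conservative; below it the SE is understated by less than 1%.
- A reader might take 1/√(1 − ICC) at face value and report a larger inflation and a break-even ICC to three decimals. With five centres and 20% dropout, neither is supported.
- A reader might infer that power falls below the promised 80%. That needs 5.5 to be a within-centre SD, in which case planned power would be 79.6-80.1% at ICC 0.05 and 78.1-78.4% at ICC 0.10. Protocol 11.1 gives one SD and mentions no centre component, so the documents do not support that reading.

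**Conclusion.** The point holds as a minor, inexpensive improvement. The analysis does not follow the stratified design, and ML is an odd partner for Kenward-Roger. The two small errors oppose each other, leaving a net SE error of about 1% or less up to an ICC of 0.05 and roughly 2-4% on the conservative side at 0.10. The gain from putting both right is about 0.5-1 power point at an ICC of 0.05 and about 1.5-2 at 0.10, with a test close to 5% at any ICC.

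These sizes rest on an assumed ICC, on 5.5 being the total SD, on dropout being random, and on about 156 completers. The unsettled choice between fixed and random site in the sensitivity model is a small loose end of its own, and it should be closed before unblinding in any case.

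**What to change.** In SAP 6.3.3:

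- Add centre as a five-level fixed effect to the primary MMRM and replace ML with REML, keeping Kenward-Roger. Make the two changes together, for the reason in step 6.
- Treat centre × visit as an optional refinement. It matters only if centre effects change across visits.
- Make the model without centre the sensitivity analysis. This also disposes of the open choice between fixed and random site.
- Since the imputed data sets are analysed with the same MMRM, add centre to the imputation variables for consistency.

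In SAP 6.3.4, use the same terms for the continuous secondary outcomes. The binomial identity-link models are told to take the MMRM's covariates, so state explicitly that centre need not enter them, because extra terms make non-convergence more likely.

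The cost is SAP wording, plus 4 degrees of freedom (4 per visit if centre × visit is used). If centres do not differ at all, about 0.5 power points are lost, mostly because ML's slight anti-conservatism goes. Sample size, visits and data collection do not change. Protocol 11.2 provides for a final SAP before database lock and code breaking, which is the place to do this.

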6.3.4 Analyses for Secondary Outcome

Efficacy analyses for all secondary outcomes will be performed in the ITT population, without imputation of missing data.

The same approach for the primary outcome will be used in other continuous outcomes such as SSSQ for symptom severity, physical function. Categorical data will be compared between groups using a generalized linear model with a binomial distribution and identity link that will include the same covariate as the MMRM model. In addition to the proportion of participants who were somewhat satisfied and very satisfied based on the satisfaction domain of the SSSQ, we will be analysis use the generalized linear model with the same covariate as the MMRM model. Patients' expectations of acupuncture for general disease and for DLSS, blinding, adherence data will present for descriptive purposes only.

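### The primary MMRM holds the baseline-RMDQ slope equal at weeks 6, 18 and 30, so the week-6 contrast is adjusted with a pooled slope; adding baseline × visit is a nearly free improvement

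*Combined protocol and SAP*

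**What the plan says.** In SAP 6.3.3 the response is defined so that "the observed change from baseline score at each scheduled post-baseline visit will be the dependent variable". Besides week 6, the post-baseline visits are fixed by protocol 3.4: "Timepoints 3 and 4 will be scheduled at weeks 18 and 30, respectively, during 24-week follow-up period". Three visits therefore enter the model.

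On the fixed effects the SAP states: "The model will include the baseline RMDQ score as a fixed effect, with categorical factors for treatment group (acupuncture and SA), visit", followed by the treatment × visit interaction. Of that interaction it says: "The interactions will remain in the model regardless of significance". The contrast is taken visit by visit: "Treatment group comparisons at each visit will be estimated by differences between least squares (LS) means from the treatment" × visit term. The covariance is left free: "An unstructured covariance pattern will be used to estimate the variance–covariance of the within-subject repeated measures".

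The same fixed effects carry over elsewhere. In the imputation sensitivity analysis, "each of the hundred multiple imputation datasets will be analyzed using the MMRM model". The centre sensitivity analysis only adds site. For the secondary outcomes, SAP 6.3.4 says: "The same approach for the primary outcome will be used in other continuous outcomes such as SSSQ for symptom severity, physical function". Nowhere do the documents add a baseline × visit term.

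**The concern.** The treatment effect may differ at each visit, but the baseline coefficient may not. The only confirmatory visit is week 6, the end of treatment. The other two visits fall 12 and 24 weeks after treatment stops (18 − 6 and 30 − 6).

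The slope of change on baseline equals the slope of the follow-up score on baseline minus 1, so it moves if the association with baseline weakens or strengthens over time. If it does move, the single fitted slope is a compromise that need not suit week 6.

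Two things are then at stake: how fully a chance imbalance in baseline RMDQ is removed from the week-6 difference, and a small amount of avoidable residual variance at week 6. No planned analysis relaxes the equal-slope restriction.

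**Working it through.** **Planned sample size.** Protocol 11.1 gives a difference of 2.5, SD 5.5, two-sided 5%, 80% power and 20% dropout. The normal approximation is n = 2 × (1.960 + 0.842)² × 5.5² / 2.5² = 76 per arm, and 76 / 0.80 = 95. The t-based version gives 77 per arm, and 77 / 0.80 rounds up to 97, or 194 in total, close to the stated 196. With 78 evaluable per arm (80% of 98), power is 81.0% (normal) or 80.5% (t). The calculation uses neither the baseline covariate nor the repeated measures, so the term at issue does not affect N.

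**Formulas** (large sample, complete data, n evaluable per arm). Let b6, b18 and b30 be the true slopes, s the baseline SD, Δ the chance baseline difference between arms, and Σ the 3 × 3 residual covariance of the fitted model.

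- Common slope: bc = (1′Σ⁻¹b) / (1′Σ⁻¹1), a weighted combination of all three slopes.
- Error left in the week-6 contrast for a given imbalance: (b6 − bc) × Δ. Since Δ averages zero under randomisation, this is not a bias.
- Extra variance of the week-6 contrast: (b6 − bc)² × s² × 2/n.

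**Assumed inputs.** The documents supply none of these: s of 4 to 5, residual correlations of 0.5 to 0.85, and the slopes in the table. The 5.5 is taken as the SD of the week-6 change (the protocol does not say whether it refers to the score or the change), with n = 78.

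**Worked case.** Slopes −0.3/−0.5/−0.6, s = 4, correlation 0.7.

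- The weights are 0.26/0.28/0.46, so bc = 0.26(−0.3) + 0.28(−0.5) + 0.46(−0.6) = −0.494, and b6 − bc = 0.194.
- Week-6 residual variance with its own slope: 5.5² − 0.3² × 4² = 28.81. Extra: 0.194² × 16 = 0.60. SE ratio: √(29.41 / 28.81) = 1.010.
- A 1.96-SE imbalance is 1.96 × 4 × √(2/78) = 1.26 points (1.57 for s = 5). The error left is 0.194 × 1.26 = 0.24 points.

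**Range over s = 4 and 5 and correlations 0.5 to 0.85**

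| Slopes at weeks 6/18/30 | Weight of week 6 in the common slope | Week-6 SE, common ÷ visit-specific | Power, visit-specific vs common | Error at 1.96-SE imbalance (points, absolute) |
|---|---|---|---|---|
| Equal | 0.36 to 0.37 | 1.000 | same | 0 |
| −0.3/−0.5/−0.5 | 0.10 to 0.31 | 1.005 to 1.014 | 82.9–83.9% vs 82.3–83.2% | 0.17 to 0.28 |
| −0.3/−0.5/−0.6 | 0.03 to 0.30 | 1.009 to 1.031 | 82.9–83.9% vs 81.7–82.7% | 0.23 to 0.41 |
| −0.6/−0.4/−0.3 | 0.43 to 0.80 | 1.002 to 1.010 | gain of 0.5 points or less | 0.08 to 0.21 |
| −0.2/−0.5/−0.7 (extreme) | −0.11 to 0.26 | 1.026 to 1.114 | 81.8–82.3% vs 73.6–79.8% | 0.39 to 0.83 |

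In the middle of the grid (s = 4.5, correlations 0.5 to 0.8) the moderate patterns cost about 0–2% of the SE. The 3% value needs s = 5 together with correlation 0.85.

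**Validity check by simulation** (600 trials per case, 98 per arm, s = 4.5, correlation 0.7, slopes −0.3/−0.5/−0.6 or −0.6/−0.4/−0.3). With dropout completely at random or dependent on baseline, the two models' mean week-6 estimates agree within 0.01. Rejection under the null is 0.047–0.063 with the common slope and 0.043–0.063 with visit-specific slopes; the Monte Carlo error is √(0.05 × 0.95 / 600) = 0.009. Only when dropout depended on baseline in opposite directions by arm did the two models differ systematically, by about 0.07–0.12 points.

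**The case against.** The best defence is that the primary test is sound as written. Any fixed baseline coefficient leaves a randomised contrast unbiased on average, and the unstructured covariance carries the extra week-6 variance into the reported standard error. The documents do not say that the slopes differ, and with equal slopes nothing is lost. In the moderate scenarios power moves by about one point or less, and an imbalance as large as 1.96 SE arises by chance in only about 5% of trials. All of this stands.

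A reader might also infer more than the text supports:

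- *That the slope is taken from follow-up in place of week 6.* It is pooled. Week 6 contributes, with weight 0.43–0.80 if slopes flatten and 0.03–0.30 if they steepen moderately.
- *That the slope must steepen over time.* This is plausible if the association with baseline decays, but the documents contain no data on it.
- *That this is the model's only restriction.* It also assumes a linear baseline effect and the same baseline slope in both arms.
- *That follow-up data would stop influencing week 6 once the term is added.* With missing week-6 values, later visits inform week 6 in any MMRM under missing at random.

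The defence does not give a reason to keep the restriction. In none of the slope patterns examined was the SE materially better with the common slope, and choosing the term after seeing a baseline imbalance would be a data-driven change to the primary model.

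**Conclusion.** The point holds as a low-cost refinement. The SAP fixes one baseline slope across all three visits, so the confirmatory week-6 contrast uses a pooled adjustment. It would be wrong to read this as a biased or invalid primary test: under randomisation the contrast stays essentially unbiased and type I error stays near 5%. The one systematic difference found needed dropout related to baseline in opposite directions by arm.

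If the slopes differ moderately, a 2-SE imbalance leaves an error equal to about 3–16% of the 2.5-point target (0.08 / 2.5 to 0.41 / 2.5), and the SE loss is small. Larger losses require extreme slope differences. The absence of the term is certain from the text. Its size is not, because the baseline SD, the slopes and the correlations are all assumed.

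**What to change.** In SAP 6.3.3, add the baseline RMDQ × visit interaction to the fixed effects and state that it is retained regardless of significance, as is already done for treatment × visit. Use the same term in the MMRM fitted to the imputed data sets and in the site sensitivity model. Under SAP 6.3.4, use the corresponding baseline × visit term for each continuous secondary outcome that has a baseline value.

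Make the change before database lock and code breaking, the point by which protocol 11.2 requires the final SAP. The cost is one phrase in the SAP, one term in the model statement and two parameters (three slopes instead of one). The sample size stays at 196.
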